6.0 Number of Subjects

We will recruit 64 child/caregiver dyads (for a total of 128 people) seeking outpatient treatment at MUSC for acute burn injury.

Consistent with the intent of a feasibility RCT, sample size for this study was determined for pragmatic reasons rather than through formal power calculation. Following the recommendations by Kraemer et al. [73] as well as the CONSORT 2010 statement extension to randomized pilot and feasibility trials [74] the purpose of feasibility/pilot studies is to test recruitment processes, feasibility of the intervention and measurement as well as training protocols, data collection, and data quality control, storage and retrieval processes. Further, Kraemer et al. advise that effect size estimates obtained from pilot studies have insufficient accuracy as useful input for sample size determination for future study design.

We anticipate high feasibility of recruitment of 64 pediatric patient/caregiver dyads with partial thickness burns over 24 months. Our TOBI pilot included recruitment of 32 patient/caregiver dyads, and this recruitment was completed over 9 months with minimal infrastructure. With ~200 outpatient pediatric partial thickness burns cases per year at MUSC and our track record of enrolling participants into clinical studies (including TOBI pilot), an enrollment of ~25% of this sample of ~275 is highly feasible. We had a 74% participation rate in the TOBI pilot, 3-4 times higher than what is needed to meet proposed targets.

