10.0 Study Design / Methods

The RCT will include 64 patient/caregiver dyads recruited from the MUSC outpatient burn clinic, hospital floor, or pediatric emergency room, randomized to burn care enhanced with TOBI (n=32) or FTF standard care (n=32). After obtaining informed consent, the research staff will create a new patient record in the REDCap database and assist (if needed) the caregiver in completing the initial questionnaire battery using the REDCap survey. The baseline questionnaires, completed by the caregiver, will include the demographics form, measures about attitudes toward telemedicine, perception of healthcare access, affect, depression, anxiety, self-efficacy, and peritraumatic distress (see measures attached). All PHI will be protected by a study ID to promote confidentiality. The family will receive a ClinCard at the beginning of the study which works like a bank debit card and can be used to purchase goods or services everywhere Debit MasterCard is accepted. Each time they receive payment for participation in this study, the money will be added to the card. Families will receive \$20 for completion of baseline assessment.

At the completion of questionnaires, caregivers will be randomly assigned to treatment conditions. Stratified permuted block randomization will be used to assign patients to either the burn care enhanced with TOBI or FTF care only (32 dyads per arm). Assignment will be stratified by provider to ensure balanced enrollment across the treatment arms regardless of numbers enrolled per provider. To minimize the likelihood that the blind will be broken, i.e. the next treatment assignment can be guessed, the block size will be varied.

Chart review will be conducted within approximately 72 hours of enrollment and data will be recorded in a chart review checklist and subsequently transferred into the database (e.g., burn mechanism, % TBSA, burn location, burn depth, date of burn injury, time to medical treatment, type of first clinical encounter [burn outpatient vs. emergency department vs. hospital discharge], and type of dressing).

Patients randomized to FTF will undergo standard burn care including a return follow-up in the burn clinic on a routine basis as prescribed by the clinical burn team (e.g., at least once per week) until the burn has healed. Healing is defined as greater than 95% epithelialization of the burn wound. This will be determined by a clinician.

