Patients randomized to burn care enhanced with TOBI will be given instructions and will be aided in downloading TOBI onto their smartphones. Patients with TOBI will be able to use standard FTF care as well. They will demonstrate an ability to use the various components of TOBI during initial visit and enrollment and will be explained how to contact the burn team through the hospital paging operator if TOBI is unavailable. Similar to the FTF group, they will be given oral and written instructions about standard burn care with routine clinical care delivered via TOBI, including a plan to interface with the burn clinicians (text messaging, videoconferencing, or image transfer) on a routine basis. TOBI patients will be scheduled for weekly videoconferencing encounters through the app until the burn has healed. Patients will be asked to come in-person if would complications are noted by a clinician (e.g., non-healing, infection). If technological problems with TOBI are encountered (e.g., video stops working), providers may switch to another secure telehealth platform to provide the necessary care and will document technology issues appropriately, as part of feasibility assessment.

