Clinical data will be collected on case report forms by the clinical care team (e.g., burn nurse, physician) and entered into the REDCap database in a coded manner by a research assistant (who is blind to the treatment condition to reduce bias during data entry) at clinically determined intervals per routine care based on clinical judgment with TOBI or FTF (see table below). The duration and number of clinical encounters for both conditions will be guided by best clinical practice and each patient's needs. On average, most burns that meet the study eligibility criteria require 2-5 visits and heal within 2-4 weeks. Case report forms will be generated with study ID only, with no identifiable PHI in order to protect patient's privacy. Data collected at intervals will include adherence to prescribed wound care, change in therapy, wound complications, day of healing, pain scores, sleep problems, unexpected return to clinic or emergency room (see Clinical Case Report Form attached). App metrics, such as number of videoconferences, number of text-messages, number of photos, and scripted messages by burn professional will be recorded by the app software and exported at the end of the study. Images of wounds will not be stored for the purposes of this study. They may be uploaded by clinical care team members into the patient's medical record as part of standard care procedures (outside of the study). Adherence to therapy will be defined as parent/patient performance of prescribed wound care through the end of treatment. Overall compliance with therapy is defined as documentation of healed burn through TOBI or FTF. Clinical data collection will continue until 1 month after the burn is diagnosed as healed by a burn physician in either condition (FTF or TOBI).

At 1-month, caregivers will be asked to complete the post-treatment questionnaires by phone or virtually using the REDCap survey, using a public link and study ID to identify their survey. This assessment will include measures about attitudes toward telemedicine, perception of healthcare access, affect, depression, anxiety, perceived stress, posttraumatic growth, treatment satisfaction, and app feasibility (TOBI only group) (see measures attached). Collected data will be entered into REDCap by the study staff. Overall, participation rate will be recorded. Families will receive \$30 following completion of post-treatment assessment.

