focus on variability and precision of estimates rather than magnitude of effect sizes. 95% confidence intervals (CIs) of the difference in mean days to healing (or treatment change/infection) between interventions will be obtained. In addition, survival distributions and their 95% CIs will be obtained for each intervention arm using the Kaplan-Meier product limit method. Further, 95% CIs for hazard ratios will be obtained using Cox proportional hazards regression to model time to healing (treatment change) as a function of the intervention. In the future RCT, generalized linear mixed models (GLMM) will be used to obtain estimates of the variances of the clinical outcomes and the covariance structure of longitudinal measures as critical input information for determination of sample size (and hence adequate power) [82, 83]. Frequency distributions of AEs and SAEs will be used to characterize each intervention group. Analyses of caregiver data will include pre- and post-treatment group differences (TOBI vs. FTF) to understand factors related to caregiver well-being and adjustment following mHealth burn treatment and possible predictors of outcomes. These analyses may include mixed design repeated measures analyses of variance (ANOVAs) and regressions.

When the study is concluded, after 6 years all records related to the study will be destroyed. Furthermore, all staff will sign confidentiality agreements, and training sessions will emphasize the critical importance of confidentiality. The likelihood that these methods will effectively protect the confidentiality of participants is considered to be extremely high. Based on our experience with previous research projects, it is believed that these procedures will be effective in protecting confidentiality of subjects and minimizing any potential risk from participation.

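### Time to healing is dated at near-weekly assessments but analysed by ordinary Cox regression with no tie or interval-censoring method, so a real hazard ratio would be pulled toward 1

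*Combined protocol and SAP*

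**What the plan says.** Section 11.0 (Quantitative analyses) lists three summaries of time to healing. The first is a 95% interval for the difference in mean days. The second is Kaplan-Meier: "survival distributions and their 95% CIs will be obtained for each intervention arm using the Kaplan-Meier product limit method". The third is Cox: "95% CIs for hazard ratios will be obtained using Cox proportional hazards regression to model time to healing (treatment change". The section says these analyses "focus on variability and precision of estimates rather than magnitude of effect sizes". It names no tie method, no grouped-time or interval-censored method, and no day zero for counting days to healing. Section 10.0 mentions statistical software only by example, so tie handling is left to the package default.

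Section 10.0 describes how healing comes to be observed. A clinician decides whether the wound meets the epithelialization threshold. In the app arm, "TOBI patients will be scheduled for weekly videoconferencing encounters through the app until the burn has healed". In the face-to-face arm, children return "on a routine basis as prescribed by the clinical burn team (e.g., at least once per week) until the burn has healed". It adds that "most burns that meet the study eligibility criteria require 2-5 visits and heal within 2-4 weeks". Section 11.0 confirms that the healed or not-healed decision is taken at routine intervals by clinical judgement.

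**The concern.** With two to five visits per child and roughly weekly looks, the healing date is the date of the first visit at which the wound is seen to be healed, and many children can share it. Cox partial likelihood is built for continuous times with few ties. With many ties, the approximation used for them begins to drive the answer. The Breslow form keeps every child who heals at a visit in the risk set for all the other healings at that visit, which pulls the log hazard ratio toward zero and misstates its variance. Efron corrects most of this but not all.

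This does not depend on the arms being seen at different frequencies. It arises with identical schedules, where the difference in mean days is essentially unaffected because both arms carry the same delay to the next visit. At stake are the hazard ratio and its interval, which this section presents as information on precision.

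**Working it through.** **Inputs from the documents.** Sample size: "randomized to burn care enhanced with TOBI (n=32) or FTF standard care (n=32" (Section 10.0). Visits at least weekly, two to five per child, healing mostly in 2 to 4 weeks (Section 10.0). Most pediatric partial thickness burns healed by 14 days (Section 2.0). First evaluation up to 72 hours after injury (Section 5.0). The plan gives no hazard ratio, event count or power for healing, so there is no planned figure to reproduce.

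**Scale.** If all 64 children heal, SE(log HR) ≈ √(4/64) = 0.25. The 95% interval is then the estimate divided and multiplied by exp(1.96 × 0.25) ≈ 1.63.

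**Why Breslow misstates the SE.** Suppose d of n children at risk heal at one visit and the true HR is 1. With p the treated share of those at risk, Breslow information is d·p(1−p). The actual variance of the score is d·p(1−p)·(n−d)/(n−1). For that visit the ratio of model SE to true SD is √[(n−1)/(n−d)]. With 32 of 64 healing together this is √(63/32) ≈ 1.40.

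**Simulation.** 32 per arm, Weibull proportional hazards, everyone heals, and healing is dated at the first visit on or after true healing. Assumed, not in the documents: median 14 or 16 days, shape 2 or 3 (three combinations on the strict grid), true HR 1, 1.5 or 2. There were 1,500 runs per setting (600 for the grouped-time model). Schedules in the table are identical in both arms. Day-level variation means visits off by 1 to 2 days and/or a 0 to 3 day entry offset.

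| | Strict weekly | Weekly with day-level variation |
|---|---|---|
| Distinct healing dates (mean) | 4.1–5.6 | about 11–27 |
| Largest tie, of 64 | 23–32 | 6–14 |
| True HR 1.5, Breslow | 1.25–1.32 | 1.32–1.46 |
| True HR 1.5, Efron | 1.40–1.46 | 1.40–1.49 |
| True HR 2, Breslow | 1.46–1.58 | 1.65–1.91 |
| True HR 2, Efron | 1.76–1.89 | 1.81–1.98 |

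**On the log scale, strict grid, true HR 1.5.** ln 1.5 = 0.405. Breslow recovers ln 1.25 = 0.223 to ln 1.32 = 0.278, which is 55% to 69% of it. Efron recovers ln 1.40 = 0.336 to ln 1.46 = 0.378, which is 83% to 93%.

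**Standard error and coverage, strict grid.** Breslow model SE is 0.25–0.26 against an empirical SD of 0.16–0.19, a ratio of about 1.4 (0.254/0.188) to 1.6 (0.259/0.164). Its coverage is 99.6–99.9% at HR 1, 97–98% at HR 1.5 and 87–93% at HR 2. Efron coverage is about 94–97%. At HR 1 neither method is biased.

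**More frequent looks.** With visits every 3.5 days in both arms, a true 1.5 becomes 1.37–1.40 (Breslow) or 1.48–1.50 (Efron).

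**Alternative.** A grouped-time complementary log-log model on the strict weekly grid gives 1.52–1.56 for a true 1.5 and 2.07–2.09 for a true 2. Its model SE is 0.27–0.31 and its coverage 93–96%.

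**The case against.** The strongest reply is that the documents do not describe a strict weekly grid. Face-to-face visits have a weekly minimum, and Section 2.0 puts general practice at one to three per week. Data are collected at intervals set by clinical judgement. App families also exchange messages and images between video visits, and Section 14.0 speaks of daily digital interactions. Entry is spread over up to three days after injury, and the case report form has a field for the day of healing. A reader might infer that healing must fall on three or four dates. That is not established: even the strict grid averaged 4 to 6, and day-level variation gave about 11 to 27. This part of the reply stands, and it shrinks the problem. It does not remove it, because no section says how a healing day between clinician assessments would be established.

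A reader might also infer that any Cox interval here would be wrong. The calculations do not support that. The misstated SE belongs to Breslow; Efron coverage is close to nominal. Efron's loss at a true HR of 1.5 on the strict grid is 0.405 − 0.378 = 0.03 to 0.405 − 0.336 = 0.07 on the log scale, about 0.1 to 0.3 of the 0.25 standard error.

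A third tempting inference is that a shrunken hazard ratio would inflate an event-driven sample size for the next trial. Section 6.0 says "sample size for this study was determined for pragmatic reasons rather than through formal power calculation" and goes on to cite advice that pilot effect sizes are too inaccurate to size a later study. No event-driven design is planned, so that harm is not claimed.

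Finally, unequal assessment frequency between arms could do more damage. With looks every 3.5 days in one arm and weekly in the other, a true HR of 1 came out at 0.72–0.74 or 1.37–1.40, and Efron did not repair it. That is a separate matter and does not justify leaving the tie method open.

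**Conclusion.** The point holds in a limited form. Healing is observed in intervals and the planned model ignores this. If visits are effectively weekly in both arms and Breslow ties are used, a real effect is substantially attenuated and the reported precision is wrong: the interval is too wide at HR 1 and under-covers at HR 2. With Efron ties the attenuation is modest and coverage near nominal. With irregular visit days both effects shrink. If there is no effect, the hazard ratio is not biased, and the mean difference is sound when schedules are equal.

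The consequence is confined to one of three planned displays, in a trial that tests no healing hypothesis. It still matters because that display is offered as evidence on precision, and under Breslow precision is what goes wrong. All sizes rest on assumed healing distributions and hazard ratios, complete healing and no dropout; the 20% attrition benchmark in Section 4.0 was not modelled.

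**What to change.** In Section 11.0, state the time origin for days to healing. Define each child's outcome by two dates: the last assessment at which the wound was not healed and the first at which it was. Children who leave before healing contribute their last not-healed date. Analyse these with an interval-censored proportional hazards model. If visits prove effectively weekly, a grouped-time model (discrete-time regression with complementary log-log link) is a simple alternative whose hazard ratio has the same meaning. Fixed weekly windows should not be imposed on irregular visits, because they discard recorded dates and were not tested there. The interval-censored model was not simulated here; it is recommended because it matches how the data arise. If Cox is kept as a display, name Efron or exact ties, not Breslow.

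The cost is one or two sentences and two dates taken from assessments that already take place, with no added visits. The reported standard error rises slightly: about 0.27–0.31 for the grouped-time model against 0.25–0.26 for Cox on the same weekly data. The grouped-time model also overshoots a little at this sample size (1.52–1.56 for a true 1.5).

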12.0 Provisions to Monitor the Data to Ensure the Safety of Subjects

Adverse events (AE), serious adverse events (SAE), and unanticipated problems (UPs) will be monitored throughout the study and any event will be followed to resolution or stabilization. [name] is an experienced surgeon specializing in burns, and [name], one of [name] mentors, is a licensed clinical psychologist with extensive experience treating victims of traumatic events. In addition to reporting of AEs to MUSC's IRB within 10 days, routine reporting of AEs using NIH's standard AE forms will occur semiannually as determined with NIH staff and the Data and Safety Monitoring Board. All SAEs will be reported immediately to the IRB and the federal funding agency. We will report any unanticipated problems (UPs) to the IRB during Continuous Review and in NIH progress reports unless they are also AEs or SAEs, in which case we will report these events as described above. The Principal Investigator will provide continuous, close monitoring with prompt reporting of adverse events to the IRB and NIH, and will follow MUSC's adverse event reporting policy.

In addition, a Data and Safety Monitoring Board (DSMB) will be formed to ensure the ongoing safety of the participants. Should we encounter AEs, SAEs, or UPs, such as worsening of symptoms or distress, patients may be hospitalized for higher level of care and may undergo an operation if the burn converts to a deeper burn or if an infection occurs. A patient may also need to be escalated to inpatient care due to distress during wound care. The PI will appoint members from diverse disciplinary backgrounds that are not involved in the project. The chairperson of this committee will be [name], PhD. [name] is a full professor and Vice Chairman for Research in the Department of Surgery. He has held numerous grants and has expertise in monitoring clinical trials. Dr.

[name] has agreed to serve as the biostatistician on the DSMB. [name] is a staff scientist and statistician in the Cardiovascular Research Laboratory at MUSC. [name] has agreed to serve as the expert in the therapeutic area of burn surgery. [name] is a burn and trauma surgeon in the Department of Surgery, with an active research interest in firearm injury prevention. The Board will monitor subject participation and safety issues with a focus on study enrollment in process, study safety, and data integrity. They will be sent tables with de-identified data prior to each semiannual meeting for their review. For the duration of the RCT, including the follow-up, the board will meet semiannually to review data and monitor any potential concerns that have developed. Safety monitoring will involve review of cases involving AEs or UPs where continuing the intervention could create safety concerns, ongoing review of potential risks and our measures in place to protect participants against foreseeable risks, review of consent procedures, and review of participant privacy protections and security of data collected by our system. MUSC will have full and instant access to all reports and data reviewed by the DSMB. This will ensure adherence to the monitoring plan and requirements for reporting AEs, SAEs, and UPs. The PI also will have the ability to call an unscheduled in-person meeting in the event of any AEs, UPs, or SAEs that arise with the project. The Board also will be responsible for following up on requested actions based on recommendations from the Board in response to an AE. Outcome of SAEs will be written in the form of a report reported to the MUSC IRB and NIH.

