14.0 Risks to Subjects

1. The research material obtained from human participants in this protocol will include questionnaire data and case report forms clinical data. Breaches of confidentiality are a concern with web-accessible components of any study. However, we have taken many steps to protect participant information, including only using study ID numbers on all questionnaires and storing data on secure, password-protected servers. Only the study team will be able to see this information.
2. It is possible that the questionnaires may make participants feel upset. These reactions will be normalized and appropriate resources and/or referrals to a mental health provider (outside of the study) may be provided.
3. Risks associated with TOBI vs. standard FTF burn care:
 - We do not anticipate more than minimal risk to participants in this study as study procedures closely follow those used in routine clinical care. Because the intervention includes the use of a smartphone technology in addition to standard therapy FTF therapy if needed, there is minimal risk above the risk normally incurred by undergoing standard medical treatment. A potential risk is the possibility that burn care delivered through TOBI is worse than care delivered in person (FTF). Although numerous studies suggest that the burn care can be

safely delivered through telemedicine, the TOBI intervention may not accurately portray the burn injury. In practice, the TOBI arm of the RCT includes the use of a smartphone technology in addition to standard therapy. Because patients in the TOBI arm are allowed to return in person for FTF care, there is minimal risk above the risk normally incurred by undergoing standard medical treatment. For example, it is possible that a participant might experience a burn complication at home that is not properly detected through use of the TOBI intervention. Burn complications include infection, pain, and non-healing. If there is an issue with technology, or image/video transfer is inadequate, these issues will be noted and the patient will be evaluated in the standard manner, in clinic face-to-face or in the emergency department. Patients in the standard therapy arm will be evaluated in clinic or emergency room, which is the standard of care. Nevertheless, we do have a specific protocol should a participant have an adverse event as a result of participation in this study.

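### An unanticipated problem that has not yet caused harm reaches the IRB later than a minor adverse event, and no rule sends SAEs to the DSMB between its semiannual meetings

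*Combined protocol and SAP*

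**What the plan says.** Section 12.0 sets a different reporting speed for each class of event.

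- AEs: "In addition to reporting of AEs to MUSC's IRB within 10 days, routine reporting of AEs using NIH's standard AE forms will occur semiannually".
- SAEs: "All SAEs will be reported immediately to the IRB and the federal funding agency". On their follow-up: "Outcome of SAEs will be written in the form of a report reported to the MUSC IRB and NIH". Neither sentence names the DSMB.
- UPs: "We will report any unanticipated problems (UPs) to the IRB during Continuous Review and in NIH progress reports". Those that are also AEs or SAEs follow the two rules above. No number of days is given for the rest.

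On the DSMB, the same section says "the board will meet semiannually to review data and monitor any potential concerns that have developed", and of its material, "They will be sent tables with de-identified data prior to each semiannual meeting for their review". The Board's remit includes AE and UP cases in which going on with the intervention might be unsafe, as well as privacy and data security. The PI may call an unscheduled meeting after any AE, UP or SAE. No trigger or deadline is attached to that power.

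Section 14.0 opens its list of risks with confidentiality: "Breaches of confidentiality are a concern with web-accessible components of any study". It also relies on an in-app question about recent fever to reduce the chance that a wound infection is missed through TOBI.

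**The concern.** In a trial of an app, some problems arise before anyone is harmed: a data breach, images that do not arrive, a safety prompt that fails to appear. Such a fault can touch many families at once. If it is classed as a UP and no child has yet had an adverse event, Section 12.0 gives it the slowest route to the IRB. A minor AE in one child has a 10-day limit; the fault waits for the next Continuous Review. The section's undertaking to report promptly, and the institutional policy that it cites, are both worded for adverse events and so do not clearly close the gap.

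A smaller gap concerns the DSMB. It is set up to protect participants while the trial runs, yet its only fixed supply of information is the set of tables before each semiannual meeting. Section 10.0 expects most eligible burns to heal in 2 to 4 weeks, so most children enrolled early in a six-month interval would finish treatment before the Board next meets.

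**Working it through.** **The rules side by side**

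| Event | To the IRB | To the DSMB |
|---|---|---|
| AE | within 10 days | tables before semiannual meetings |
| SAE | immediately (and to the funder) | no time set; PI may call a meeting |
| UP that is not an AE or SAE | at Continuous Review (and in NIH progress reports) | no time set; PI may call a meeting |

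The late UP route is a stated rule, not an omission. The missing SAE link to the DSMB is an omission.

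**Inputs**

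- 64 dyads over 24 months (Section 6.0), allocated 32 and 32 (Section 10.0).
- Pilot recruitment: 32 dyads in 9 months (Section 6.0), used as a faster scenario.
- DSMB interval: 6 months (Section 12.0).
- Continuous Review interval: not stated. I show 6 and 12 months as assumptions.
- Uniform accrual is assumed.

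**The plan's own figures.** 32 + 32 = 64. At the pilot rate, 64 / (32/9) = 18 months, so the planned 24 months is consistent with the pilot. The documents give no figure for enrolment between safety reports.

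**Formula.** TOBI dyads enrolled in one full interval = monthly accrual × months × 1/2; share of arm = that number / 32.

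- Planned rate: 64/24 = 2.67 per month.
  - 6 months: 16 dyads, 8 TOBI, 8/32 = 25%.
  - 12 months: 32 dyads, 16 TOBI, 16/32 = 50%.
- Pilot rate: 32/9 = 3.56 per month.
  - 6 months: 21.3 dyads, 10.7 TOBI, 33%.
  - 12 months: 42.7 dyads, 21.3 TOBI, 67%.

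**Which figure belongs to which gap**

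- SAE to DSMB: the interval is 6 months, so 8 to about 11 TOBI dyads (25% to 33%).
- UP to IRB: 8 to about 11 if Continuous Review is six-monthly; 16 to about 21 (50% to 67%) if yearly.

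**Average wait.** These are full-interval figures. A problem arising at a random time waits half an interval on average. At the planned rate that is 4 TOBI dyads for 6 months and 8 for 12 months; at the pilot rate, about 5 and 11.

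**Comparison with the 10-day limit.** Taking 24 months as about 730 days, 64/730 × 10 = 0.88 dyads, or 0.44 in the TOBI arm. At the pilot rate, with 9 months as about 274 days, 32/274 × 10 = 1.17 dyads, or 0.58 in the TOBI arm. Under a 10-day limit, fewer than one TOBI dyad would be expected to enrol before the IRB is told.

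**The case against.** The strongest reply is that enrolment before a report is not the same as exposure to an unmanaged problem. The PI monitors continuously. TOBI families keep access to face-to-face care (Sections 10.0 and 14.0). Providers may move to another secure platform, and families can reach the team through the paging operator (Section 10.0). Once a fault causes harm it is an AE or SAE and is reported quickly. All of this stands and limits the harm to an individual child. It does not tell the IRB about a fault or breach that affects many families and has not yet produced an event.

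Nor is it certain that the examples are UPs. Technology failure is a feasibility endpoint in Section 4.0 and confidentiality breach is a listed risk in Section 14.0, so both are foreseen in some degree. The protocol never says when either counts as a UP. The examples must therefore stay conditional; the reporting rule is the same whatever the example.

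Institutional requirements that are not in the documents may set a faster route. That is possible, but the protocol as written states the slower one.

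For SAEs the objection is stronger. A reader might infer that SAEs go without outside review for six months. The documents do not support that: the IRB and the funder are told at once, and what is missing is the copy to the Board. A reader might also infer that only the PI can convene the Board. Section 12.0 gives the PI that power but does not make it exclusive, and it requires Board members who are not involved in the project.

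**Conclusion.** The point holds in two parts of unequal weight.

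The main part is the UP rule. Followed exactly, Section 12.0 brings a not-yet-harmful problem to the IRB later than a minor AE. The size depends on the unstated Continuous Review interval and on accrual: from a quarter to a third of the TOBI arm over a full six-month interval, and from half to two thirds over a full yearly one, with half those numbers on average.

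The lesser part is that no rule brings SAEs to the DSMB between meetings, which corresponds to 25% to 33% of the TOBI arm per full interval. The stated earlier route is at the PI's discretion.

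It is tempting to combine the two and say that up to half the TOBI arm could enrol before the Board hears of an SAE. The documents do not support this. Half belongs to the UP-to-IRB gap alone, at the planned accrual rate and with an assumed yearly review. Even there it is not a maximum, since the pilot rate gives 67%.

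This affects safety oversight. It does not touch the sample size or the analysis.

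**What to change.** Amend Section 12.0 in two places.

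1. Report every UP to the IRB within the same 10 days as AEs, whether or not harm has occurred. A UP that is also an SAE stays on the immediate route.
2. When an SAE, or a UP involving TOBI function or data security, is sent to the IRB, copy it to the DSMB chair at the same time.

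It would help to add a line saying when an app fault or a confidentiality breach is to be classed as a UP. Letting the chair decide whether to hold an unscheduled review is a governance preference and can be offered as optional.

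The cost is a few sentences, a few extra reports and possibly a short remote review by a Board that is already planned.
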